### 2.2 Background

#### 2.2.1 Congenital Adrenal Hyperplasia

CAH is a chronically debilitating autosomal recessive genetic disorder caused by a critical enzymatic deficiency in the steroidogenic pathways that synthesize the corticosteroids aldosterone and cortisol within the adrenal gland ([White and Speiser, 2000; Bachelot et al, 2008](#)). CAH is typically classified as either classic (the more severe form that is usually detected

in infancy) or nonclassic (the milder form that may not become evident until childhood or early adulthood). Classic CAH can be further sub-classified as salt-wasting or simple virilizing. Approximately 75% of CAH patients have a mutation that leads to severe aldosterone deficiency, resulting in the salt-wasting form of CAH characterized by the loss of large amounts of sodium via their urine (hyponatremia), hyperkalemia, and elevated plasma renin activity indicating hypovolemia, leading to dehydration and hypotension that can be life threatening in early infancy. The remaining 25% of CAH patients produce sufficient aldosterone to avoid neonatal adrenal crisis but are nevertheless debilitated by the simple virilizing form of CAH resulting from impaired cortisol production. Cortisol deficiency, a hallmark of CAH, disrupts the balance of the HPA axis by removing the negative feedback to the hypothalamus provided by normal levels of cortisol. This leads to the overproduction of CRF by the hypothalamus, the consequent overproduction of ACTH by the pituitary gland, and the resulting adrenal hyperplasia and overproduction of cortisol precursors by the adrenal gland. Because CAH patients are deficient in enzymatic activity that converts cortisol precursors to cortisol, these precursors are funneled into the biosynthetic pathway for adrenal androgens, leading to androgen overproduction. Androgen excess may result in precocious puberty; seborrhea; impaired fertility; irregular menses, amenorrhea, acne, hirsutism, and virilization in females; and TARTs in males.

The most common genetic cause of CAH, accounting for over 90% of cases, is mutation of the *CYP21A2* gene, which encodes the cytochrome P450c21 enzyme, commonly known as 21-hydroxylase, which is required for the synthesis of cortisol and aldosterone from the precursors 17-OHP and progesterone (White and Speiser, 2000; Bachelot et al, 2008; Auchus, 2015; Doleschall et al, 2014). Mutations in genes that encode other enzymes critical in steroidogenesis (*CYP17A1*, *HSD3B2*, *CYP11B1*, and *POR*) contribute to the remaining 5% to 10% of CAH cases (Turcu and Auchus 2015). Severe mutations that completely ablate 21-hydroxylase activity lead to the salt-wasting form of CAH. Milder mutations that result in even 1% to 2% residual 21-hydroxylase activity enable sufficient aldosterone production to avoid neonatal adrenal crisis and produce the simple virilizing form of CAH. Neonatal screening of 17-OHP to diagnose CAH is now performed in the United States and many other countries, with the goal of reducing mortality and morbidity due to salt-wasting adrenal crises in newborns (Falhammar et al, 2015). A 17-OHP level >300 nmol/L is indicative of untreated CAH, and the patient is then generally genotyped to confirm the diagnosis and to help determine treatment approaches (Falhammar et al, 2015; Choi et al, 2016).

Evidence-based treatment guidelines for CAH are only beginning to be developed (Reisch, 2015), and current overall treatment effectiveness for CAH patients is poor (Mnif et al, 2012; Bachelot et al, 2015). Current treatment for CAH is centered around providing pharmacologic (supraphysiologic) doses of glucocorticoids (e.g., hydrocortisone) to replace cortisol. In patients with the salt-wasting form of CAH, mineralocorticoids (e.g., fludrocortisone) are also used to replace aldosterone; before weaning, salt supplements (NaCl) are also provided to prevent a potentially lethal salt-losing crisis. The challenge in using glucocorticoid therapy to manage CAH lies in its narrow therapeutic window and in striking the difficult balance between hyperandrogenism and hypercortisolism. Up to 70% of patients with CAH are considered

outside the acceptable bounds of biochemical control ([Han et al, 2014](#)). Among patients with 21-hydroxylase deficiency treated with glucocorticoids, normal serum androstenedione has been shown to be achieved in only 36% of patients ([Arlt et al, 2010](#)). Under-treatment carries the risk of adrenal insufficiency and crisis (dehydration, hypotension, hypoglycemia) and allows androgen overproduction (precocious puberty, female virilization, TARTs, infertility). In contrast, over-treatment with glucocorticoids may suppress growth and cause iatrogenic Cushing's syndrome, producing such metabolic symptoms as hypertension, greater BMI, obesity, hypercholesterolemia, and insulin resistance. Over a lifetime, the treatment of patients with CAH shifts from an emphasis on normal childhood growth to pubertal development to adult fertility and long-term health concerns, including metabolic abnormalities, cardiovascular disease, osteoporosis, and overall diminished quality of life ([Auchus, 2015](#); [Arlt et al, 2010](#)).

Numerous studies have documented diminished quality of life in patients with CAH ([Han et al, 2013](#); [Aulinas and Webb, 2014](#); [Gilban et al, 2014](#); [Hummel et al, 2016](#)). Faced with the debilitating effects of the disease itself, ineffective treatment, and/or the severe side effects of long-term high-dose glucocorticoid treatment, CAH patients may develop depression and anxiety. Patients with CAH have increased mortality, with 1 study documenting a mean age of death of 41.2 years in patients with 21-hydroxylase deficiency. The causes of death were adrenal crisis (42%), cardiovascular disease (32%), cancer (16%), and suicide (10%) ([Falhammar et al, 2014](#)).

Refer to the Investigator's Brochure (IB) for additional information on CAH.

## **2.2.2 SPR001 for the Treatment of CAH**

SPR001 is being studied for the treatment of CAH on the basis of its ability to antagonize CRF1 receptors located on the pituitary gland, thereby reducing the hypothalamic drive of CRF on the pituitary, consequent ACTH overproduction by the pituitary, and consequent 17-OHP and androgen overproduction by the adrenal glands. This mechanism of action has been validated in a previous proof-of-concept study using a similar small-molecule CRF1 receptor antagonist, which produced reductions in ACTH and 17-OHP in subjects with CAH ([Turcu et al, 2016](#)). In vitro studies show that SPR001 binds to CRF1 receptors with high affinity and specificity and blocks CRF1-mediated receptor function.

The safety profile of SPR001 has been established in nonclinical toxicology studies and in 2 completed Phase 1 clinical studies in healthy volunteers. A Phase 2 study in subjects with CAH (Study SPR001-201) is currently ongoing.

## **2.2.3 Nonclinical Toxicology of SPR001**

The nonclinical safety profile of study drug substance (SPN001) has been evaluated in repeat-dose range-finding and definitive toxicology studies in rats and dogs administered SPN001 orally once daily for up to 91 consecutive days at doses up to 2000 mg/kg/day. In rats, SPN001-related findings were limited to the testes at 2000 mg/kg/day and the liver of both sexes at 5, 20, and 2000 mg/kg/day. The no observed adverse effect level (NOAEL) for SPN001 in rats was considered to be 20 mg/kg/day in males and 2000 mg/kg/day in females. In dogs, SPN001-related findings were limited to the testes at 2000 mg/kg/day, the liver of both sexes at

70 and 2000 mg/kg/day, and the thyroid gland of both sexes at 2000 mg/kg/day. The NOAEL for SPN001 in dogs was considered to be 70 mg/kg/day in both sexes. All findings in both species were reversible following a 6-week washout period. Refer to [Section 2.3.1](#) for a discussion of the potential liver, testicular, and thyroid risks associated with SPR001.

In reproductive and developmental toxicity studies, no adverse effects on fertility or early embryonic development were noted when SPN001-treated male rats (dosed at 5, 20, or 1000 mg/kg/day) were mated with untreated female rats or when SPN001-treated female rats (dosed at 20, 300, or 1000 mg/kg/day) were mated with untreated male rats. The NOAEL for SPN001 for male and female reproductive function was considered to be 1000 mg/kg/day. In an embryo-fetal development study conducted in rabbits (dosed at 30, 100, or 1000 mg/kg/day), developmental toxicity, which occurred concomitantly with maternal toxicity, was noted at 100 and 1000 mg/kg/day. Effects included increases in resorptions and post-implantation loss and corresponding reductions in litter sizes and live fetuses at 1000 mg/kg/day and lower fetal body weight, a greater number of multiple morphological alterations, and reduced ossification in some bones of the paws at 100 and 1000 mg/kg/day. The NOAEL for developmental toxicity was considered to be 30 mg/kg/day.

In a study conducted in juvenile rats administered SPN001 at 100, 300, or 1000 mg/kg/day for 7 weeks beginning on postnatal day 45 (comparable to a 12-year-old human), adverse effects were limited to microscopic findings in the testes of males at 1000 mg/kg/day. These findings included minimal or mild bilateral tubular degeneration within the seminiferous tubules and scattered focal loss of various cell types, often segmental within a tubule, that lacked stage or cell-type specificity. Corresponding minimal luminal debris and reduced sperm within the epididymides were also noted. The NOAEL for SPN001 in juvenile rats was considered to be 300 mg/kg/day in males and 1000 mg/kg/day in females.

In addition, a complete battery of standard genotoxicity tests consisting of in vitro bacterial reverse mutation and chromosome aberration assays and an in vivo (rat) bone marrow micronucleus assay has been conducted. A bovine corneal opacity and permeability assay has also been conducted.

#### **2.2.4 Clinical Experience with SPR001**

In 2 completed Phase 1 studies, a total of 53 healthy adult subjects aged 21 to 64 years were treated with at least 1 dose of SPR001. The first-in-human study of SPR001 (Study I3C-FW-BLA) evaluated single ascending doses of 2 mg to 800 mg. In this study, a small number of subjects experienced diarrhea and headache of mild or moderate severity. A subsequent study (Study I3C-FW-BLAB) evaluated repeat doses of 50 mg, 150 mg, or 200 mg SPR001 once daily for 14 consecutive days. A small number of subjects in the repeat-dose study experienced dyspnea, rhinorrhea, palpitations, and headache. The Phase 1 studies showed no clinically significant alterations in safety laboratory values, vital signs, or ECGs. SPR001 was well tolerated in healthy human subjects, with no SPR001-related SAEs / AEs leading to discontinuation or DLTs.

An ongoing Phase 2, open-label, proof-of-concept study (Study SPR001-201) is currently evaluating the safety and efficacy of SPR001 in adults with classic CAH. Cohort A of Study SPR001-201 has been completed, with 10 subjects receiving at least 1 dose of SPR001 and 9 subjects completing the cohort. Dosing for each subject in Cohort A was to start at 200 mg QD (for 14 days) and to escalate to 600 mg QD (for 14 days), then 1000 mg QD (for 14 days). Preliminary safety data from Cohort A shows SPR001 to be generally well tolerated through 600 mg QD and 4 weeks of dosing, with no SAEs, AEs leading to discontinuation, DLTs, or AESIs and no meaningful changes across clinical laboratory, ECGs, the Beck Depression Inventory-II (BDI-II) and C-SSRS, or physical examination findings. Refer to [Section 2.3](#) for preliminary safety and efficacy data from Cohort A that speaks to the potential clinical risks and benefits of SPR001 as a treatment for CAH. In Cohorts B/C/D of this study, approximately 3 to 6 subjects are expected to be enrolled into each cohort with a 2-week treatment period. Study drug dosing will begin at 200 mg BID in Cohort B and may be adjusted in Cohorts C/D based on an adaptive multiple ascending dose design.

### 2.3.2 Known Potential Benefits

Evidence from nonclinical and early clinical studies suggests that SPR001 is effective as a CRF1 receptor antagonist, a mechanism of action that supports the clinical investigation of SPR001 for the treatment of CAH. This mechanism of action has been validated in a previous proof-of-concept study using a similar small-molecule CRF1 receptor antagonist, which produced reductions in ACTH and 17-OHP in subjects with CAH (Turcu et al, 2016). Preliminary data from Cohort A of Study SPR001-201 show clinical evidence of CRF1 receptor target engagement (reductions in ACTH) and reductions in key adrenal hormones (17-OHP and androstenedione) at all dose levels tested.

### 2.3.3 Assessment of Potential Risks and Benefits

Multiple study design elements have been incorporated to mitigate the potential risks of LFT laboratory abnormalities, testicular injury, and thyroid effects described in [Section 2.3.1](#). Because these risks are all associated with higher doses of SPR001, study drug will initially be administered in this study at 400 mg QD, which is within the range of clinical precedence that has been safe and well tolerated. Additionally, clinical laboratory measures of liver chemistry, testicular function, and thyroid function will be assessed every 2 weeks throughout the treatment period of this study. Liver chemistry will be monitored by measuring ALT, aspartate aminotransferase (AST), alkaline phosphatase (ALP), gamma-glutamyltransferase (GGT), and total and direct bilirubin. Testicular function will be monitored by measuring LH, FSH, inhibin B, and SHBG; performing scrotal ultrasounds; and conducting semen analysis. Thyroid function will be monitored via a thyroid panel that measures T3, T4, and thyroid-stimulating hormone (TSH). Finally, strict individual treatment stopping criteria for liver chemistry findings and a criterion for increased liver chemistry monitoring are in place (see [Section 7.2.1](#) and [Section 12.2](#)).

The mild and reversible toxicologic effects of SPR001 on the male reproductive tract in nonclinical studies occurred in the context of animals with normal, rather than elevated, baseline hormone function. As a CRF1 receptor antagonist, SPR001 is intended to reduce abnormally elevated ACTH and androgen levels. In nonclinical models where baseline hormone levels are within normal ranges, clinical benefits are not expected, and indeed, toxicities may be expected as a result of androgen reduction outside of the normal range. However, in patients with CAH, whose baseline ACTH and androgen levels are pathologically elevated, androgen reduction would be considered a positive, therapeutic effect.

The Sponsor believes that the benefit-to-risk profile of this study is favorable. Given the serious nature of CAH and the limitations and risks of chronic steroid therapy, new treatment modalities are needed for patients with CAH. Given 1) the acceptable safety and tolerability profile of SPR001 in healthy volunteers from the Phase 1 program and in subjects with CAH administered study drug at up to 600 mg QD in Cohort A of Study SPR001-201 and 2) the preliminary evidence of reductions in ACTH, 17-OHP, and androstenedione at all dose levels tested in Cohort A of Study SPR001-201, the Sponsor believes that the benefit-to-risk profile favors the continued investigation of SPR001 and the investigation of extended treatment with SPR001 for up to 3 months in subjects with CAH.

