#### **7.2.4 Adrenal Insufficiency Stopping Criteria**

If a subject dosed with study drug exhibits clinically significant signs of acute adrenal insufficiency, such as postural hypotension, nausea, and abdominal pain, the Investigator should consider withholding the subject's dose(s) of SPR001, initiate appropriate corticosteroid therapy, and contact the Medical Monitor. If there is no clear explanation for the subject's acute adrenal insufficiency, such as inadequate corticosteroid replacement dosing or low circulating levels of plasma cortisol, the Investigator should review the subject with the Medical Monitor for possible study drug discontinuation.

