#### **7.2.7 Potentially Clinically Significant Adverse Events**

Clinically significant AEs include but are not limited to SAEs ([Section 8.2.2](#)), AEs leading to study drug discontinuation/study withdrawal, DLTs ([Section 7.1](#)), and AESIs ([Section 8.2.8](#)) that are each considered at least possibly related to study drug. The occurrence of any clinically

significant AE will receive special consideration in decisions regarding continuation or suspension of dosing or enrollment and will be reported to the SRC within 1 day of awareness for immediate review.

Section 12.3 also provides a list of signs and symptoms (Section 12.3.1) and a list of laboratory findings (Section 12.3.2) that constitute potentially clinically significant AEs not otherwise specified among the foregoing individual treatment stopping criteria. These provide guidelines for a level of moderate-severe abnormality in safety findings that could cause harm to subject health and may preclude further study drug dosing. These lists are intended to guide the Investigator and are not meant to be a set of absolute criteria. Safety parameters not included in the list may be interpreted in a similar fashion according to Investigator judgment. Common Terminology Criteria for Adverse Events (CTCAE) severity grading should also be referenced (Section 8.2.3.1).

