### **8.2.8 Adverse Events of Special Interest**

AESIs are those AEs that do not meet SAE criteria but must be monitored on an ongoing basis. These events will be reported on the SAE Report Form, allowing for the collection of additional information, as warranted. The following will be considered AESIs for this study:

- Suicidality as indicated by type 3, 4, or 5 ideation on the C-SSRS (see [Section 7.2.3](#) regarding study drug stopping criteria and [Section 8.1.6.1](#) regarding the C-SSRS). This should be reported as an AESI until it becomes serious according to the SAE definition (e.g. hospitalization).
- High HADS score or other indication of worsening depression (see [Section 7.2.5](#) regarding study drug discontinuation and [Section 8.1.6.2](#) regarding the HADS)
- Significant liver chemistry changes that do not satisfy stopping rules (see [Section 7.2.1](#) and [Section 12.2.1](#)). Cases of Hy's Law should be reported as SAEs.
- Severity Grade 3 or higher TEAE considered related to study drug (see [Section 7.1](#) regarding dose reduction)

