### **8.2.9 Disease-Related Events**

The following disease-related events are common in patients with CAH, and this should be taken into consideration when evaluating the causality of AEs during the study:

- Acute encephalopathy
- Adrenal crisis or insufficiency
- Avascular necrosis
- Memory impairment
- Dizziness
- Dyslipidemia; hyperlipidemia
- Dyspepsia
- Elevated fasting serum leptin and insulin concentrations and insulin resistance
- Gastrointestinal effects, including gastritis, peptic ulceration, and gastrointestinal hemorrhage
- Headache
- Hyper- or hypokalemia; hyper- or hyponatremia
- Hyper- or hypoglycemia; impaired glucose tolerance
- Hyper- or hypotension
- Impaired exercise tolerance
- Infertility
- Ischemic heart disease, subclinical atherosclerosis
- Lower bone mineral density
- Myopathies
- Obesity
- Psychiatric disorders, substance use disorders, mood swings, challenges with social interactions
- Seizures have been reported during episodes of hyponatremia and of hypoglycemia
- Weakness / lethargy / fatigue

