8.1. Adverse Event Preferred Term and Body/Organ System Summary Tables

Adverse events will be coded to the preferred terms of the Medical Dictionary for Regulatory Activities (MedDRA®). Summaries will present by system organ class (SOC), preferred term (PT) and severity and/or relatedness, the frequency and percentage of subjects reporting each observed event.

A treatment-emergent adverse event (TEAE) will be defined as any AE that begins on or after the date of first dose of study drug up to the date of last dose of study drug plus the number of days in the follow-up period. AEs observed during the period from obtaining informed consent to the start of administration of study drug will be regarded separately from TEAEs.

All AEs and all TEAEs will be listed by subject.

Subjects who experienced treatment-limiting AEs will be listed. Treatment-limiting AEs are defined as any event that leads to permanent or temporary discontinuation from treatment, or a reduction in the treatment dose.

Summary of adverse events will be dependent on adverse events observed. If no adverse events meeting a specific table are observed, the summary table will not be completed. Blank summary tables will not be utilized.

The following is the list of adverse event tables:

Overall:

- Overall Summary of Adverse Events

Label	Reporting Format
Adverse Event	F
Moderate or Severe Adverse Event	F
Adverse Event Related to Study Drug	F
Moderate or Severe Adverse Event Related to Study Drug	F
Serious Adverse Event	F
Serious Adverse Event Related to Study Drug	F
Adverse Events Leading to Permanent Study Drug Discontinuation	F
Adverse Events Leading to Temporary Interruption of Study Drug	F
Death During Study	F

By preferred term:

- Treatment-emergent Adverse Events by PT
- Treatment-emergent Adverse Events by SOC and PT

By severity:

- Treatment-emergent Adverse Events by SOC, PT and Severity
- Serious Adverse Events
- Deaths during Study

By relatedness:

- Drug-Related Treatment-emergent Adverse Events by SOC and PT
- Drug-Related Treatment-emergent Adverse Events by SOC, PT and Severity
- Drug-related Serious Adverse Events

Other:

- Adverse events leading to premature study drug discontinuation

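### Acute adrenal insufficiency is foreseen on drug but is not an AESI and has no grouped count; the gap this leaves is narrow and cheap to close

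*Protocol*

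**What the plan says.** **Risk section.** Protocol 2.3.1 describes liver, testicular and thyroid findings, and 2.3.3 sets out mitigation for those three: "Multiple study design elements have been incorporated to mitigate the potential risks of LFT laboratory abnormalities, testicular injury, and thyroid effects".

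**Event foreseen on drug.** Section 7.2.4 is a titled stopping section for a dosed subject who "exhibits clinically significant signs of acute adrenal insufficiency, such as postural hypotension, nausea, and abdominal pain". Section 7.1 also allows study drug or glucocorticoid to be changed for such signs.

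**Special-interest list.** In 8.2.8 the words "The following will be considered AESIs for this study" introduce four entries: C-SSRS type 3 to 5 ideation, high HADS or worsening depression, liver changes short of the stopping rules, and a related TEAE of Grade 3 or higher. Adrenal insufficiency is not listed.

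**Attribution.** Section 8.2.9 lists adrenal crisis or insufficiency, and separately dizziness, hypotension, sodium, potassium and glucose disturbances and weakness, as common in CAH. It says that "this should be taken into consideration when evaluating the causality of AEs during the study". The first paragraph of 7.2.7 covers events "that are each considered at least possibly related to study drug".

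**Reporting.** AESIs are part of the primary endpoint (Protocol 3), and 9.3.5 promises a summary of them. SAP 8.1 tabulates by preferred term, for example "Treatment-emergent Adverse Events by SOC and PT". Neither 8.1 nor the index in 11.3 has an AESI table or a grouped adrenal category.

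**The concern.** The subjects are cortisol-deficient and the drug is intended to reduce ACTH drive, so adrenal insufficiency is an obvious event to follow. The protocol provides for handling it but not for counting it.

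Two features combine. First, the DLT definition and the only AESI route open to an adrenal episode both depend on a judgement of relatedness, while 8.2.9 asks investigators to bear in mind that the event is common in the disease. Table 2 in 8.2.3.2 points the same way: one criterion for an unlikely relationship is that the subject's clinical state could readily have produced the event. A single-arm trial has no control group against which to check that judgement. Second, 7.2.4 describes the event by its signs. If a site records signs rather than the diagnosis, one episode is divided among several preferred-term rows.

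At stake is the readability of the primary safety result. With 11 subjects, one or two divided episodes are easy to overlook.

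**Working it through.** The plan gives no figure to reproduce. The check is to follow one episode through each reporting route.

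| Route | Condition for entry | Relatedness required? | Reaches a non-serious episode, judged disease-related, with no study drug change? |
|---|---|---|---|
| SAE (Protocol 8.2.2, 8.2.6) | Serious | No | No |
| DLT (7.1) | Grade 3 or higher, at least possibly related | Yes | No |
| AESI (8.2.8) | Fourth bullet only: Grade 3 or higher, related | Yes | No |
| Drug-related tables (SAP 8.1) | Related | Yes | No |
| Interruption and discontinuation rows, treatment-limiting listing (SAP 8.1) | Drug stopped, interrupted or reduced | No | No |
| Prompt SRC report (7.2.7, 8.2.5, 12.3) | Clinically significant or potentially so | Yes in the first paragraph of 7.2.7; not stated for the 12.3 lists | Possibly, sign by sign, at the 12.3 thresholds |
| TEAEs by SOC and PT (SAP 8.1) | Any TEAE | No | Yes, but labelled adrenal only if the diagnosis was the reported term |

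The uncounted case must therefore meet four conditions together: non-serious, judged disease-related, recorded by signs, and no interruption, reduction or discontinuation of study drug. An episode met only by a glucocorticoid change is an example. Such changes are recorded (6.5.1), and SAP 6.6.3 defines hydrocortisone equivalents, but no table in 11.3 is titled for on-study glucocorticoid change; only prior glucocorticoid therapy has its own table.

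**Parity with other stopping topics.** Section 7.2 has six titled topics: liver, QT, suicidality, adrenal, depression and reproductive hormones. Three (liver, suicidality, depression) have a matching AESI bullet: 3/6.

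**Illustration, with assumed counts.** Input: n = 11 (SAP 4.3). Assume two subjects with one episode each, recorded as three signs.
- No sign shared: 2 × 3 = 6 preferred-term rows, each 1/11 = 9.1% (exact 95% CI 0.2% to 41.3%).
- All signs shared: 3 rows, each 2/11 = 18.2%, but none labelled adrenal insufficiency.
- Grouped row in either case: 2/11 = 18.2% (exact 95% CI 2.3% to 51.8%).

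**What a grouped count could show.** The documents give no event rate. For assumed true risks of any episode of 5%, 10% and 20%, the chance of at least one affected subject is 1 − (1 − p)^11 = 43%, 69% and 91%. If none is seen, the one-sided 95% upper bound is 1 − 0.05^(1/11) = 23.8%. The row would be descriptive only.

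**The case against.** The case against is strong, and most of it limits the point.

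- **The risk is managed.** A reader might infer from 2.3.3 that adrenal insufficiency is left uncovered. That is not supported. Sections 7.1, 7.2.4 and 12.3 address it, and vital signs, electrolytes, fasting glucose, renin, aldosterone and background glucocorticoid levels are measured every two weeks. Section 2.3.1 describes findings from earlier studies, and the documents report no adrenal insufficiency there. The omission concerns naming and counting.
- **Many disease-attributed episodes are caught.** A reader might infer that any non-serious episode judged disease-related escapes every special category. It does not. SAP 8.1 has a temporary-interruption row and a treatment-limiting listing, neither dependent on causality, and withholding or reducing drug is among the responses that 7.1 names. This stands, with one qualification: the 11.3 index contains a listing only for premature discontinuation, though it may be updated.
- **A reported diagnosis has its own row** whatever the attribution, and nothing directs sites to record signs. This stands; fragmentation is a possibility.
- **Section 8.2.9 steers less than it seems.** It does not tell investigators to judge events unrelated. Nausea and abdominal pain, two of the three signs in 7.2.4, are not named there, although dyspepsia and other gastrointestinal effects are.
- **The mortality figures do not bear on this.** Section 2.2.1 attributes 42% of deaths in one cohort to adrenal crisis and 10% to suicide, and only suicidality is an AESI. It is tempting to read those percentages as the size of the gap. They describe deaths in an outside cohort. A fatal or life-threatening crisis is an SAE regardless of causality, and the figures say nothing about non-serious episodes.
- **Parity is weak.** QT and reproductive hormones also have stopping sections and no AESI bullet.
- **Episodes can be reconstructed** from by-subject listings at n=11. True, but only by unplanned reading, which a prespecified row replaces.

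**Conclusion.** The point holds as an inexpensive improvement to reporting, not as a failure of safety monitoring. The protocol foresees acute adrenal insufficiency on drug, yet does not name it as a risk, list it as an AESI or give it a grouped count. The consequence is confined to the four-condition case above.

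Its frequency cannot be estimated from the documents, and the 2/11 example rests on assumed counts and assumed sign-by-sign recording. The documents do not show that any episode would be missed; they show that one could be left without an adrenal label. The change is worth making because safety is the primary objective, the data are already collected, and an AESI summary has been promised but is absent from the SAP.

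**What to change.** 1. **Protocol 8.2.8:** add as an AESI *adrenal insufficiency or adrenal crisis, including any episode handled under 7.1 or 7.2.4 as acute adrenal insufficiency, regardless of causality*.
2. **SAP 8.1 and 11.3:** add the AESI summary promised in Protocol 9.3.5. Add one grouped row and a by-subject listing, *adrenal insufficiency episode*, defined as any TEAE coded to adrenal insufficiency or crisis, or any episode handled under 7.1 or 7.2.4. Count subjects regardless of causality, separately on drug and after last dose; the split fits the interest in HPA-axis rebound in Protocol 4.2. Include serious episodes in this row, because 8.2.8 reserves the AESI label for events that are not SAEs.
3. **Supportive listing:** show AEs with a glucocorticoid start or increase separately, with the recorded reason for use. Keep this out of the definition, since a steroid given for an unrelated AE would otherwise be called an adrenal episode.
4. **Protocol 2.3.1 and 2.3.3:** name the risk.

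The AESI bullet alone would yield no count while the SAP lacks an AESI table, so item 2 is essential. SAP 4.3 already states the final sample size; items 2 and 3 can be built from recorded AEs, glucocorticoid changes and Medical Monitor contacts, with the episode list fixed before database lock.

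The cost is one bullet, one AESI summary, one row, two listings, a few sentences and possibly a few more expedited forms. The downside is that the AESI count may rise and will include disease-driven episodes that a single-arm trial cannot separate from drug effect. How episodes are treated does not change.
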